4.1 Description of protocol design

4.1.1 Phase 0

In the proposed trial, patients will be administered ribociclib+everolimus prior to surgical resection of their tumor. Recurrent GBM patients will be randomized into one of the three time-interval cohorts for the first two dose levels.

In the lead-in dose escalation study, the first six subjects (lead-in) will receive ribociclib 400 mg and everolimus 2.5 mg orally-administered in 5 daily doses with the last dose. If one or less patient experiences DLT among the 6 patients, this regimen with ribociclib 400 mg and everolimus 2.5mg will be considered safe and we will continue with the dose escalation phase of the study up to Level 6.

Four dose escalation levels:

Level 0: ribociclib 400mg and everolimus 2.5

Level 1: ribociclib 600mg and everolimus 2.5mg

Level 2: ribociclib 600mg and everolimus 5mg

Level 3: ribociclib 600mg and everolimus 10mg

Level 4: ribociclib 600mg daily for 5 days and everolimus 50mg given once on Day 5.

Level 5: ribociclib 600mg daily for 5 days and everolimus 60mg given once on Day 5.

Level 6: ribociclib 600mg daily for 5 days and everolimus 70mg given once on Day 5.

Three to fourteen (3-14) patients will be enrolled into each level to observe AEs and DLTs. Detailed DLTs definition will be summarized in [Table 9](#).

All patients will receive ribociclib and everolimus orally-administered in 5 daily doses.

Cohort 1: last ribociclib+everolimus dose 1 to 3 hours prior to craniotomy for tumor resection (n=8 patients)

Cohort 2: last ribociclib+everolimus dose 7 to 9 hours prior to craniotomy for tumor resection (n=8 patients)

Cohort 3: last ribociclib+everolimus dose 23 to 25 hours prior to craniotomy for tumor resection (n=8 patients)

In Dose Level 0 three to six patients will be enrolled into the time interval cohorts, sequentially whenever possible (e.g. cohort 1, cohort 2, cohort 3, cohort 1...), with at least 1 patient in each of the time intervals.

In Dose Level 1

Three to six patients will be enrolled into the time interval cohorts, sequentially whenever possible (e.g. cohort 1, cohort 2, cohort 3, cohort 1...), with at least one patient in time cohort 1 and two patients in cohort 2. If there are positive PK/PD results at the Maximum Tolerated Dose (MTD) or Optimal Biological Dose (OBD) dose level, the dose level will be expanded to 8 additional patients with 4 patients in each time cohort 1 and 3 (Sections [6.1.2](#) and [6.1.2.1](#)).

In Dose Levels 2+, three to six patients will be enrolled into cohort 2. If there are positive PK/PD results at the Maximum Tolerated Dose (MTD) or Optimal Biological Dose (OBD) dose level, the dose level will be expanded to 8 additional patients with 4 patients in each time cohort 1 and 3 (Sections [6.1.2](#) and [6.1.2.1](#)).

Dose Level	Time Interval	N=	Dose Expansion Cohort N=	Time Cohort Expansion N=
Level 0	Cohort 1	2	N/A	N/A
	Cohort 2	2		
	Cohort 3	2		
Level 1	Cohort 1	1	0	4
	Cohort 2	2	3	0
	Cohort 3	0	0	4
Level 2	Cohort 1	0	0	4
	Cohort 2	3	3	0
	Cohort 3	0	0	4
Level 3	Cohort 1	0	0	4
	Cohort 2	3	3	0
	Cohort 3	0	0	4
Level 4 - 6	Cohort 1	0	0	4
	Cohort 2	3	3	0
	Cohort 3	0	0	4

To assess the PK and PD endpoints listed above, blood, CSF and brain tumor tissue will be collected intraoperatively (enhancing and non-enhancing tumor tissue will be collected and analyzed separately).

Additionally, blood samples will be obtained on Day 4 in Dose Levels 1-3 (the day before the surgery for Cohorts 1 & 2; 2 days before surgery for Cohort 3) at pre-dosing (trough level), 0.5, 1, 2, 4, 7, and 24 hours post dose. (Note: 24 h sample is the pre-dosing (trough level) blood sample on Day 5).

Dose Level 4+ only: PK blood sampling will occur on Day 5: pre, 0.5, 1, 2, 4, 6, 8 and 24 hours post-dose (Note: 24 h sample is the pre-dosing (trough level) blood sample on Day 6).

Dose Levels 0-3:

[figure not shown]
PHASE 0 STUDY COHORT 1										
DAY 4 PRE- DOSE	Time 0	30 min	1 hour	2 hours	3 hours	4 hours	7 hours	24 hours ± 1 h	POSTOP- Phase 2	
Blood			Blood	Blood	Blood		Blood	Blood	Blood	
DAY 5 PRE- DOSE	Ribociclib + everolimus								Ribociclib + everolimus	
Blood			Blood* CSF* Tumor*							

PHASE 0 STUDY COHORT 2										
DAY 4 PRE- DOSE	Time 0	30 min	1 hour	2 hours	4 hours	7 Hours	8-9 Hours	24 hours ± 1 h	POSTOP- Phase 2	
Blood			Blood	Blood	Blood	Blood	Blood		Blood	
DAY 5 PRE- DOSE	Ribociclib + everolimus								Ribociclib + everolimus	
Blood			Blood* CSF* Tumor*							

PHASE 0 STUDY COHORT 3										
DAY 4 PRE- DOSE	Time 0	30 min	1 hour	2 hours	4 hours	7 Hours	23 -25 hours	POSTOP- Phase 2		
Blood	Ribociclib + everolimus		Blood	Blood	Blood	Blood	Blood	Blood	Ribociclib + everolimus	

Initial Version date: 10/16/2018

Revision date: 03/11/2019, 5/07/2019, 09/26/2019, 03/17/2020, 08/26/2024

[figure not shown]

Phase 0 participants who do not proceed to Phase 2 will be contacted every 3 months by letter or phone for collection of survival data for up to 5 years. The start of follow up for long-term survival begins following completion of the Day 30 safety follow up call.

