Due to persistent negative PK effects from everolimus, despite no adverse events limiting drug dosing, additional dose-levels will employ a single, high-dose administration of everolimus. Other combination drug studies have suggested 70mg weekly as a maximal-tolerated dose. As a lead-in to this combination dose in our study, a new dose level at 50mg once prior to surgery (in combination with 600mg ribociclib) will be introduced. This lead-in dose will give rise to 60mg at the next level and 70mg at the final level. Similarly, the phase 2 component of the study will reflect this new dosing regimen for patients with PK and PD effects from both drugs. Specifically, a lead-in regimen at 50mg q weekly in Phase 2 (in combination with ribociclib) will then be escalated towards 70mg weekly.

3 Objectives and endpoints

	Objective	Endpoint
Primary	
• To determine the dose-limiting toxicity (DLT) and maximum tolerated dose (MTD) for study drug when administered in combination.• To identify recurrent high-grade glioma patients with positive PK and PD effects.	
• MTD: highest dose of drug that did not cause a DLT in > 17% of participants• PK: total and unbound ribociclib and everolimus concentrations in non-enhancing and contrast-enhancing tumor tissue samples• PD: pRB-positive cells and pS6-positive cells
Secondary	
• To explore safety and efficacy in recurrent high-grade glioma patients with demonstrated PK and PD effects and determine RP2D• To describe PK for Phase 2 patients	
• Progression-free survival (PFS)• Overall survival (OS)• Drug-related toxicity• RP2D• Systemic PK profiles of ribociclib and everolimus when combined.
Exploratory	
• To explore evidence for CDK4/6 and mTOR pathway activity in tumor tissue (as compared to	
• Quantification of total and phosphorylated forms of Rb, FoxM1, S6, 4EBP, as well as cleaved Caspase-3 and MIB1. Expression of Cyclin D1,

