6.1 Protocol treatment

For this protocol, the term “treatment” refers to ribociclib+everolimus.

Table 6 Dose and treatment schedule

Study treatments	Pharmaceutical form and route of administration	Dosage Form and Strength	Frequency and/or Regimen
Phase 0			(5 day regimen)
Ribociclib (LEE011)	Tablet for oral use	200mg tablets 2.5mg tablet	Once daily
Everolimus	Tablet for oral use		Once daily or Twice daily*
Phase 2 (optional)			(28 day cycle)
Ribociclib (LEE011)	Tablet for oral use	200mg tablets 2.5mg tablet	Once daily for 3 weeks, 1 week off
Everolimus	Tablet for oral use		Once daily* or Twice daily** for 3 weeks, 1 week off

*Dose Level 4+: everolimus is taken once on Day 5 in Phase 0. In Phase 2, everolimus dose will be given weekly on Days 1, 8, 15, 22 of each cycle.

**Dose Level 3: everolimus is taken twice daily in Phase 2.

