6.1.1 Phase 0 & 2 Dose Escalation Schedule

Table 7 Dose Escalation Schedule

Dose Level	Phase 0 Dose of Study Drug ^a	Minimum Number of Patients	Phase 2 Dose of Study Drug ^a
0	ribociclib 400mg and everolimus 2.5mg	6	ribociclib 400mg and everolimus 2.5mg
1	ribociclib 600mg and everolimus 2.5mg	3	ribociclib 600mg and everolimus 2.5mg

Initial Version date: 10/16/2018

Revision date: 03/11/2019, 5/07/2019, 09/26/2019, 03/17/2020, 08/26/2024

Dose Level	Phase 0 Dose of Study Drug ^a	Minimum Number of Patients	Phase 2 Dose of Study Drug ^a
2	ribociclib 600mg and everolimus 5mg	3	ribociclib 600mg and everolimus 5mg
3	ribociclib 600mg and everolimus 10mg ^b	3	ribociclib 600mg and everolimus 10mg ^c
4	ribociclib 600mg, qd and everolimus 50mg once ^d	3	ribociclib 600mg daily and everolimus 50mg once weekly ^e
5	ribociclib 600mg, qd and everolimus 60mg once ^d	3	Cycle 1: ribociclib 600mg, qd and everolimus 50mg once weekly ^e Cycle 2+: 600 mg, qd and everolimus 60mg once weekly ^f
6	ribociclib 600mg, qd and everolimus 70mg once ^d	3	Cycle 1: ribociclib 600mg, qd and everolimus 50mg once weekly ^e Cycle 2: 600 mg, qd and everolimus 60mg once weekly ^f Cycle 3+: 600 mg, qd and everolimus 60mg once weekly ^f

- a. The Phase 0 dose given to the patient will be the RP2D. If more than one DLT is observed in 6 patients in Phase 2, the regimen at that given level will be considered as the maximal administered dose and the next lower dose level will be the MTD/RP2D for subsequent patients enrolled into Phase 2
- b. In Phase 0, the everolimus dose will be given in one dose (10mg, qd).
- c. In Phase 2, dose will be given in two doses (5mg, bid)
- d. In Phase 0, the everolimus dose will be given in one dose on Day 5 only; ribociclib dose will be given daily for 5 days.
- e. In Phase 2, everolimus dose will be given once weekly on Days 1, 8, 15, 22 of each cycle with ribociclib administered daily for 21 consecutive days and 1 rest week.
- f. If the dose is well tolerated in Cycle 1, the dose may be escalated based on investigator discretion.

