6.1.4 Dosing regimen

6.1.4.1 Ribociclib + Everolimus

The Barrow Neurological Institute / St. Joseph's Hospital and Medical Center will purchase commercially available supplies of ribociclib (Kisqali®) and everolimus (Afinitor®). Ribociclib+everolimus will be administered orally once daily on a 5-day dosing schedule during Phase 0 and a 28-day dosing schedule (3 weeks on, 1 week off) during Phase 2. The investigator must instruct the patient to take the treatment exactly as prescribed.

- Patients should take ribociclib+everolimus once daily at approximately the same time each day with a large glass of water (~ 250 ml) at the same time each day, in the morning, afternoon, or evening. The dose taken on the day of surgery will vary depending upon the planned time of the resection (see Section 4.1).
- Patients can take ribociclib+everolimus without regard to meals; however, dietary habits around the time of dosing should be as consistent as possible throughout the study.
- Patients should be instructed to swallow the ribociclib tablets whole and not to chew, crush or open them
- If vomiting occurs during the course of treatment, no re-dosing of the patient is allowed before the next scheduled dose.
- Any doses that are missed (not taken within 6 hours of the intended time) should be skipped and should not be replaced or made up on a subsequent day.
- Patients must avoid consumption of grapefruit, grapefruit hybrids, pomelos/pummelos, star-fruit, pomegranates or Seville oranges or products containing the juice of each during the entire study and preferably 7 days before the first dose of study medication, due to potential CYP3A4 interaction with the study medications. Orange juice is allowed.
- No herbal or dietary supplements known as strong inhibitors or inducers of CYP3A4 or those with a known risk of QT prolongation are permitted, due to potential interactions with ribociclib and everolimus; multivitamins are allowed.
- In Phase 2, Dose Levels 0-2, patients will take ribociclib+everolimus for 21 consecutive days followed by 1 rest week.
- In Phase 2, Dose Level 3, patients should take everolimus in two 5mg doses, approximately 12 hours apart (BID) for a total of 10mg. In Phase 0, the dose is 10mg given in one dose per day (qd).
- In Phase 2, Dose Level 4+, patients should take everolimus in one dose weekly. Ribociclib will be taken for 21 consecutive days followed by 1 rest week.

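### Three general Phase 0 sentences prescribe five everolimus doses without exempting Levels 4-6, where the regimen is a single dose on Day 5

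*Combined protocol and SAP*

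**What the plan says.** **General Phase 0 statements**

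- Section 4.1.1, after the level list: "All patients will receive ribociclib and everolimus orally-administered in 5 daily doses".
- Section 6.1.4.1: "Ribociclib+everolimus will be administered orally once daily on a 5-day dosing schedule during Phase 0".
- Section 6.5.3.1 describes Phase 0 patients as getting five consecutive doses of the combination.

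**Statements specific to Levels 4-6 in Phase 0**

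- Section 2.3 introduces these levels as additional ones built on a single high dose of everolimus, starting with "a new dose level at 50mg once prior to surgery".
- Section 4.1.1, level list: "Level 4: ribociclib 600mg daily for 5 days and everolimus 50mg given once on Day 5". Levels 5 and 6 follow the same pattern at 60 mg and 70 mg.
- Section 6.1, Table 6 footnote for Level 4+: "everolimus is taken once on Day 5 in Phase 0".
- Section 6.1.1, Table 7 note d: "In Phase 0, the everolimus dose will be given in one dose on Day 5 only", with ribociclib daily for five days.
- Section 4.1.1, sampling: "Dose Level 4+ only: PK blood sampling will occur on Day 5".

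**The concern.** The two sets of statements cannot both hold for everolimus at Levels 4-6. The general sentences are not background text. One sits in the design section and refers to all patients, one opens the dosing section, and one is the compliance section's description of what patients receive. Someone who consults only Section 6.1.4.1 or only Section 6.5.3.1 finds no Level 4+ exception for Phase 0.

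These levels carry the largest single everolimus doses in the trial, and Section 2.3 justifies them by reference to 70 mg weekly as a maximum tolerated dose. A wrong dosing rule matters more here than at 2.5 mg daily.

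**Working it through.** The plan states no figure to reproduce. The check is a comparison of texts plus one multiplication.

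**Step 1. Does any general sentence exempt Levels 4-6?**

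- Section 4.1.1: no. It refers to all patients and names both drugs.
- Section 6.1.4.1: no. Its bullets do make exceptions by level. For Level 3 it gives the twice-daily Phase 2 schedule and also restates the once-daily Phase 0 schedule. For Level 4+ its only bullet concerns Phase 2 (weekly everolimus), so it does not correct the Phase 0 sentence.
- Section 6.5.3.1: no. It names the combination and makes no distinction by level.

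**Step 2. Does any Level 4-6 passage support five everolimus doses in Phase 0?** None does. The rationale, the level list, the Table 6 footnote and Table 7 note d all give one dose. Moving Level 4+ blood sampling to Day 5 fits a single Day 5 dose. Table 10 labels the high doses as weekly, and Table 7 note e has the same doses in Phase 2 as weekly: "In Phase 2, everolimus dose will be given once weekly on Days 1, 8, 15, 22 of each cycle".

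**Step 3. Size of the discrepancy.** Cumulative Phase 0 everolimus = dose × number of doses.

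- Level 4: general wording 5 × 50 = 250 mg; level-specific text 1 × 50 = 50 mg.
- Level 5: 5 × 60 = 300 mg, against 60 mg.
- Level 6: 5 × 70 = 350 mg, against 70 mg.

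The ratio is 5 at each level. Against the 70 mg weekly figure in Section 2.3, the literal totals are 250/70 = 3.6, 300/70 = 4.3 and 350/70 = 5.0 times. These totals show only what the general sentences would mean if combined with the Level 4-6 doses. No passage pairs 50, 60 or 70 mg with daily dosing.

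**Step 4. Why the sentences probably read this way.** Section 2.3 describes Levels 4-6 as additions, and Section 4.1.1 still announces four escalation levels above a list of seven (Levels 0 to 6). It is reasonable to infer that the general sentences predate the added levels, but the documents do not say so.

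**The case against.** The strongest reply is that the regimen is already fixed where it counts. The level list stands a few lines above the sentence in 4.1.1, Tables 6 and 7 agree with it, and specific text governs general text. This stands, and it is why the point is minor. It does not make the general sentences true.

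A second reply is that Section 6.1 defines treatment as the combination, so the wording in 6.1.4.1 and 6.5.3.1 could be the name of a five-day regimen. That softens those two sentences. It does not help 4.1.1, which names each drug and gives five daily doses of both.

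Several stronger readings are tempting, but the documents do not support them:

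- **That patients are likely to be overdosed.** Days 1, 4 and 5 are dosed in clinic, patients get dosing instructions and a diary for Days 2 and 3, and the tables are unambiguous.
- **That Section 6.5.3.1 would class a correctly dosed patient as non-compliant.** It sets no threshold and no definition of non-compliance. Staff assess compliance at visits, so a compliance percentage would be the reader's own construction.
- **That the Phase 2 sentence of 6.5.3.1 is also wrong.** Its count of 21 daily doses names no drug and is correct for Level 4+ ribociclib.
- **That the home-dosing text or the replacement rule is in error.** Table 13 footnote 9 and Section 7.1.1.11 contradict nothing, and note d already implies that only ribociclib is taken on Days 2 and 3. Section 7.1.1.14 names no drug, can be met by five ribociclib doses, and leaves replacement to the Sponsor-Investigator's discretion.

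**Conclusion.** The point holds as a minor internal inconsistency. Three sentences, in Sections 4.1.1, 6.1.4.1 and 6.5.3.1, are wrong for everolimus in Phase 0 at Levels 4, 5 and 6: they imply five doses where one is intended. No sample size, error rate or endpoint is affected, and Levels 0-3 are described correctly.

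The conclusion rests on taking the level list and Tables 6 and 7 as controlling, which the rationale and the sampling schedule both support. The dosing instructions and diary given to patients are not in the documents, so whether they already state the Level 4+ rule cannot be checked.

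**What to change.** In the three sentences, limit the five-daily-dose wording for everolimus to Levels 0-3 and add: *Dose Level 4+: ribociclib daily Days 1-5; everolimus once on Day 5 only.*

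Three optional clarifications could go into the same amendment, though none corrects an error:

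- Say in the Day 2-3 home-dosing text (Table 13 footnote 9 and Section 7.1.1.11) that the Level 4+ supply is ribociclib only.
- Name the drug in the Phase 2 sentence of Section 6.5.3.1.
- Name the drug in Section 7.1.1.14, keeping replacement discretionary.

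The cost is a wording amendment that uses the regimen the protocol already states. It needs no new data, patients or procedures.

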4.1.2 Phase 2 Dose expansion

Patients with tumors demonstrating favorable PK and PD will proceed to Phase 2 Dose Expansion. In Dose Levels 1-3, patients will continue treatment with the same treatment level as given in Phase 0, patients should take the treatment continuously in 28d cycles with 3 weeks on / 1 week off after surgery. In Dose Level 4+, patients should take everolimus in one dose weekly; ribociclib will be taken for 21 consecutive days followed by 1 rest week. The dose will be per Table 7. If more than one DLT is observed in 6 patients in the Phase 2 dose expansion, the enrollment will be stopped and the previous lower dose level will be considered the RP2D and will be given for the remaining patients enrolled. If more than one DLT is occurred with the Level 0, the study will be stopped due to toxicity. Typically DLTs are defined by 1 cycle of treatment, which is 28 days. Since Phase 0 treatment is given for only 5 days, Phase 0 dose escalation will only be determined by Phase 0 DLT rules unless determined otherwise by the DSMB. Patients will be treated until unacceptable toxicity is observed, or until disease progression as assessed by radiographic or clinical metrics. Preliminary rates of progression-free survival in patients with high-grade gliomas treated with ribociclib+everolimus will be measured through radiographic and clinical response metrics, specifically Response Assessment in Neuro-Oncology (RANO) criteria and investigator discretion. Phase 2 participants will return to the clinic to monitor safety per the schedule of events until treatment is ended and will then be contacted approximately every 3 months by letter or phone for collection of survival data. The start of follow up for long-term survival begins following completion of the Day 30 safety follow up call.. All Phase 0/2 participants will be followed for survival for up to 5 years.

Common Toxicity Criteria Adverse Event (CTC AE 4.03) will be utilized to review ribociclib+everolimus treatment effects in patients with brain tumors.

Trough steady-state blood samples will be obtained on days 1, 8, 15, and 22 of cycles 1 and 2 prior to the administration of ribociclib+everolimus on that day. Note: ribociclib+everolimus will be administered in the clinics on the clinic visit days to ensure the collection of trough level samples.

PHASE 2 STUDY				
	Cycle 1 (28 d)	Cycle 2 (28d)	Subsequent cycles (28d)	End of study
Day of cycle	D1, D8, D15, D22	D1, D8, D15, D22	N/A	N/A
Blood	Trough level*	Trough level*	N/A	N/A

* Trough blood sample is collected prior to the drug administration on that day. Ribociclib is administered in the clinics on the clinic visit days.

4.2 Timing of interim analyses and design adaptations

There will be no interim analysis in the study.

4.3 Definition of end of the Study

Study end will be defined by PK/PD/PG data collection using tissue derived from the last planned patient enrolled in the study.

4.4 Early Termination

Subjects/patients may withdraw at any time or be dropped from the study at the discretion of the investigator should any untoward effects occur. In addition, a subject/patient may be withdrawn by the investigator if he/she violates the study plan or for administrative and/or other safety reasons. When a subject/ patient discontinues/withdraws prior to study completion, all applicable activities scheduled for the final study visit should be performed at the time of discontinuation. Any adverse experiences which are present at the time of discontinuation/withdrawal should be followed in accordance with the safety requirements outlined.

Subjects/patients who discontinue from the study for reasons unrelated to the study (e.g., personal reasons) will be replaced as required for the study to meet its objectives. The decision to remove a subject/patient and to replace dropouts will be made by the investigator and study statistician. The replacement will generally receive the same treatment or treatment sequence (as appropriate) as the allocation number replaced. Both the replacement and originally allocated number will be unique numbers.

5 Population

5.1 Patient population

Patients will be accrued at up to 3 sites.

The investigator or designee must ensure that only patients who meet **all** of the inclusion and **none** of the exclusion criteria are entered into this protocol.

Patients enrolled in this protocol are not permitted to participate in additional parallel investigational drug or device studies while on treatment.

Please note these are the minimum inclusion and exclusion criteria required for treatment on LEE011 + everolimus. Investigators should include disease and protocol specific eligibility criteria as applicable.

